5.0 TREATMENT PLAN

This study is a randomized, controlled trial evaluating the use of topical Caphosol therapy to prevent oral mucositis (Grade ≥ 2) in children, adolescents and young adults undergoing chemotherapy. At the time of enrollment, patients will be randomized to either the control arm or the Caphosol arm. The treatment period will extend from the start of chemotherapy and continue for 7 days after completion of chemotherapy AND until the ANC is > 500 after nadir (count recovery) or until the symptoms of oral mucositis resolve; whichever occurs last.

Treatment

Caphosol Arm: Subjects randomized to the **Caphosol Arm** will use Caphosol 4 times per day as follows:

- Each dose consists of two 15 mL syringes, to be mixed at time of administration. Caphosol must be used within 15 minutes of mixing.
 - Subjects may increase the use to 6 times per day if they have symptoms of mucositis.
- Using one of the syringes, rinse and gargle (if patient is able) for one minute and then spit. Repeat using the remaining syringe.
 - For younger patients (less than or equal to 6 years of age), volume may be reduced to two syringes containing 5-10 mL each.
 - For patients unable to successfully rinse and spit, caregivers may paint their mouth (using medical sponge swabs) with the solution two times. Prior to swabbing the patient's mouth, squirt one of the syringes into a cup and using the medical sponge, soak up the solution and use the swab to coat the inside of the patient's mouth. Repeat using the second syringe.
- Patients are to avoid other oral medications, other mouth cares and food or drink for 15 minutes after using Caphosol.

- Patients will also use Biotene (5-10 mL) to swish and spit after the 15 minutes has passed. Biotene is part of our standard of care to prevent oral infections in oncology patients.

Control Arm: Subjects randomized to the **Control Arm** will use Biotene only 4 times per day as follows:

- Use 5 to 10 mL of Biotene to swish and spit
 - For patients unable to successfully rinse and spit, caregivers may paint their mouth (using medical sponge swabs) with the solution two times. Prior to swabbing the patient's mouth, pour Biotene into a cup and using the medical sponge, soak up the solution and use the swab to coat the inside of the patient's mouth. Repeat with a second swab.

The following will be observed:

- Incidence of oral mucositis. Oral mucositis will be defined and characterized by the Common Terminology Criteria for Adverse Events (CTCAE) Version 4.0 as Grade 1-4.
- Severity of oral mucositis, according to:
 - Age-appropriate pain scales (LIKERT and FACES)
 - CTCAE V 4.0 grading
 - Total narcotic usage (both the total amounts in milligrams and the number of days the patient required intravenous narcotic therapy as well as any increase of dose above baseline for patients who are on scheduled chronic use of narcotics)
 - Number of hospital days with oral mucositis present
 - TPN use and duration

The following will be observed on all patients on the Caphosol arm, via the study diary:

- Missed doses of Caphosol and reason
- Side effects attributed to Caphosol therapy
- Use of any other oral topical agents for oral mucositis (dose, schedule, number of doses taken) such as biotene/ chlorhexidine rinses and/or magic mouthwash.
- Use of any non-narcotic pain medications for oral mucositis (dose, schedule, number of doses taken)
- Use of any narcotics for oral mucositis (dose, schedule, number of doses taken)

The following will be observed on all patients on the Biotene arm, via the study diary:

- Use of any other oral topical agents for oral mucositis (dose, schedule, number of doses taken) such as chlorhexidine rinses and/or magic mouthwash.
- Use of any non-narcotic pain medications for oral mucositis (dose, schedule, number of doses taken)
- Use of any narcotics for oral mucositis (dose, schedule, number of doses taken)

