7.1.6 Administration

Investigational Pharmacy will dispense the agent for this clinical trial and place the unit of use, (oral syringe A & B) in a baggie with label for each dose. Unit dosing the oral syringe A&B in a baggie with med label and date/time due should ensure both A&B being administered.

This process means that the product will be in the patient's med drawer with other meds. If the dosing schedule is 6 doses per day (not 4), then Investigational pharmacy would send the evening and overnight doses with regular meds and bring the AM doses up each morning. Patients who receive Caphosol in the outpatient setting will receive a home supply for 2 weeks with appropriate drug labeling and instructions for use and will be evaluated in clinic for compliance and proper administration of the agent.

Caphosol will be supplied in two 15 mL syringes per dose. These are to be mixed together within 15 minutes of dose administration. Patients are to swish and gargle (if able) one half of the mixture (approximately 15 mL) for one minute, and then spit. Immediately repeat with second half of mixture.

For patients unable to successfully rinse and spit, caregivers may paint their mouth (using medical sponge swabs) with the solution x 2. Prior to swabbing the patient's mouth, mix half of the 2, 15 mL syringes into a cup and dip swab prior to coating the inside of the patient's mouth. Repeat

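### Section 5.0 requires the two Caphosol syringes to be mixed, but its rinse and swab steps then use them one after the other, in conflict with the synopsis and 7.1.6

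*Combined protocol and SAP*

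**What the plan says.** Section 5.0 opens its Caphosol instructions with the mixing requirement: "Each dose consists of two 15 mL syringes, to be mixed at time of administration. Caphosol must be used within 15 minutes of mixing". The rinse step that follows reads: "Using one of the syringes, rinse and gargle (if patient is able) for one minute and then spit. Repeat using the remaining syringe". For patients who cannot rinse and spit, the caregiver is told to "squirt one of the syringes into a cup and using the medical sponge, soak up the solution", swab the mouth, and repeat with the second syringe. For younger children the "volume may be reduced to two syringes containing 5-10 mL each".

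Section 7.1.4 says what the syringes hold: one 15 mL phosphate solution and one 15 mL calcium solution, packaged separately. It gives the composition of Caphosol only for the mixed solution.

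Section 7.1.6 says: "Caphosol will be supplied in two 15 mL syringes per dose. These are to be mixed together within 15 minutes of dose administration". It continues: "Patients are to swish and gargle (if able) one half of the mixture (approximately 15 mL) for one minute, and then spit", followed at once by the second half. Its swab step is to "mix half of the 2, 15 mL syringes into a cup and dip swab", then repeat. The synopsis gives the same rinse method (about half of the solution, then repeat) and the same swab wording.

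**The concern.** The two syringes are not interchangeable portions of one liquid. They hold different components, and the product as the protocol defines it exists only once they are combined. A rinse with one syringe, spat out, followed by a rinse with the other is therefore not two rinses with Caphosol.

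Section 5.0 is the main treatment section for the only test product, and it covers all 48 patients planned for the Caphosol arm. If some patients used the syringes in sequence, that arm would partly test something other than the intended product, and the comparison of Grade 2 or higher mucositis would be harder to interpret. The data listed for collection would not identify those patients: the diary items in 5.0 cover missed doses, side effects and other medicines, but not how the dose was prepared. A count of doses or volume would not show it either, since both syringes would have been used.

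**Working it through.** The plan states no figure to reproduce, so the check is a comparison of the texts.

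| Step | Section 5.0 | Synopsis and 7.1.6 |
|---|---|---|
| Mixing | Required at administration; use within 15 minutes of mixing | Required in both |
| Rinse, first part | One of the syringes | About half of the mixture (15 mL) |
| Rinse, second part | The other syringe | The other half of the mixture |
| Swab, first part | One syringe emptied into a cup | Half of the two syringes mixed in a cup |
| Swab, second part | The second syringe | Repeat |

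**Volume.** Two syringes of 15 mL give 2 × 15 = 30 mL per dose, and half of that is 15 mL. One syringe is also 15 mL. The volume per rinse and per dose is the same on either description, so volume cannot settle which is meant. What differs is content: on the literal 5.0 steps, 15 mL of one component and then 15 mL of the other; in the synopsis and 7.1.6, 15 mL of mixture twice.

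**Can 5.0 be reconciled with itself?** Only if a syringe in the rinse and swab steps means a 15 mL portion of the mixture. The mixture would then have to be drawn back into two syringes, and no section describes that.

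**Young children.** Section 5.0 speaks of two syringes of 5-10 mL each, although syringes are supplied at 15 mL. Section 7.1.5 gives the total as 10-20 mL, which agrees: 2 × 5 = 10 and 2 × 10 = 20. The volumes match, but 5.0 again treats the syringes as separate portions and does not say how a reduced dose is mixed.

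**Is 7.1.6 a clean model to copy?** For rinsing, yes. For swabbing, not quite. Half of the two syringes can mean half of each (7.5 + 7.5 = 15 mL of mixture) or one of the two (15 mL of a single component). The reference to mixing favours the first, but copying the phrase into 5.0 would carry a similar ambiguity with it.

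**Time limit.** The limit of 15 minutes from mixing to use is worded that way in 5.0 and the synopsis. Section 7.1.6 expresses it as mixing within 15 minutes of giving the dose. The two are compatible.

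**The case against.** The strongest answer is that nobody reading the whole protocol would skip the mixing. It is the first instruction in the same list in 5.0, it is in the synopsis, and 7.1.6, the section devoted to administration, is explicit. The young-child bullet suggests that the drafter used syringe loosely for a portion, because the syringes it mentions are not the 15 mL units supplied. In practice, pharmacy dispenses labelled A and B pairs, outpatients receive instructions for use, and administration is checked in clinic, with evaluations at least weekly. Nothing says that patients work from 5.0.

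Much of this stands. It limits the point to a conflict in the wording and rules out any claim of demonstrated harm. It does not remove the conflict. The portion reading needs a redrawing step that appears nowhere. Pairing A and B in one bag is described as a way to ensure that both are given, which sequential use would also satisfy. Staff who check proper administration have two descriptions of it in one protocol, and families hold a two-week home supply.

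A reader might infer that 5.0 orders unmixed use, or that Caphosol patients did receive unmixed components. The documents support neither: the mixing requirement is stated, and nothing in the plan shows what patients were handed or did. It is also tempting to multiply the dosing schedule into a number of unmixed rinses, or to work out the salt concentration of each syringe. The first would restate the schedule under an assumption of none or all. The second would need each salt to sit only in its named syringe, which 7.1.4 does not say.

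**Conclusion.** The point holds as a conflict in an operative instruction, and it should be fixed. Section 5.0 requires mixing, yet its rinse and swab steps, read literally, give the phosphate and calcium components separately; the synopsis and 7.1.6 use half of the mixture twice.

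That the texts differ is certain. The size of any consequence is not: it ranges from nothing, if everyone follows the mixing bullet or if the label and instructions are correct, to an unknown number of the 48 Caphosol patients using the components unmixed. The documents do not show whether unmixed use would change efficacy or safety, so no bias, loss of power or harm is claimed. The conclusion rests on 7.1.4 for the contents of the syringes and on the absence of any redrawing step; it does not depend on any assumption about how often the text is misread.

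**What to change.** Use one instruction, identical in 5.0, 7.1.6 and the synopsis:

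- Empty both syringes into a cup and mix.
- Within 15 minutes of mixing, rinse with about half of the mixture (15 mL) for one minute and spit, then immediately repeat with the other half.
- For patients who cannot rinse and spit, swab the mouth using about half of the mixture, then immediately repeat with the other half.
- For children aged 6 or under who cannot tolerate the full volume, mix both syringes fully and use 5-10 mL of the mixture twice (10-20 mL per dose). This leaves 30 − 20 = 10 mL to 30 − 10 = 20 mL unused.

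Mixing everything first is preferable to copying the present 7.1.6 swab wording, because it removes the doubt over what half of the two syringes means and works for reduced volumes too. Section 5.2 gives the age limit for reduced volume as under 5, so it should be aligned in the same amendment.

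Check that the dose label and patient instructions carry the same text. The cost is a wording amendment with IRB review, plus that check. Sample size, randomisation and analysis do not change.

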5.1 Treatment Plan Schema

[figure not shown]

Table 1: Treatment Plan

Day	Agent/Procedure
Enrollment	Randomization to control arm or Caphosol arm
Day 1 of Chemotherapy	Start study diary IF on Caphosol Arm : Start Caphosol, 30 mL QID
Completion of Chemotherapy	Control Arm : Continue study diary and Biotene for 7 days after therapy completed AND until ANC > 500 after nadir or until mucositis resolution, whichever occurs later. Caphosol Arm : Continue Caphosol, Biotene, and study diary for 7 days after therapy completed AND until ANC > 500 after nadir or until resolution of oral mucositis; whichever occurs latest.

5.2 Dose Modifications

The dosing frequency may be increased up to 6 times daily for patients with signs or symptoms of oral mucositis. An increase in frequency of Caphosol administration up to the 6 times daily will not be considered a treatment failure.

If younger patients (< 5 years of age) are unable to tolerate the full volume, the volume may be reduced to a total of 10-20 mL per dose (5-10 mL x 2), as tolerated. For patients unable to swish and spit, caregivers may paint the Caphosol solution (using medical sponge swabs) on the oral mucosa x 2 for each dose.

5.3 Supportive Care Guidelines

Patients on study will receive the standard, recommended supportive cares based on the therapy received.

Allowed oral topical medications on study:

- Standard oral cares, such as scheduled biotene or chlorhexidine rinses
- If needed for symptom management, patients may receive topical viscous lidocaine or topical “magic mouthwash” containing lidocaine, diphenhydramine and Maalox.

5.4 Duration of Therapy

Caphosol will be initiated on Day 1 of scheduled cancer therapy and will continue for:

- 7 days after therapy completion

AND

- ANC > 500 after nadir (count recovery)*

OR

- Resolution of oral mucositis symptom*

*(whichever occurs last)

Caphosol will be continued each time the patient receives chemotherapy where eligibility criteria are met for patients randomized to Caphosol arm.

Caphosol will be discontinued for allergy or patient intolerance. Please see Section 5.6 for criteria for removal from protocol therapy and off study criteria.

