1.0 BACKGROUND

Mucositis in Children, Adolescents and Young Adults Undergoing Chemotherapy

Oral mucositis, a common and debilitating complication of cancer therapy, is an inflammatory injury to the epithelial and sub-epithelial cells of the oral mucosa. Oral mucositis is thought to develop according to a five-stage model: 1) initiation; 2) up-regulation with generation of messengers; 3) signaling and amplification 4) ulceration with inflammation; and 5) healing, and typically develops 7-14 days into a chemotherapy course (1).

The incidence and severity of oral mucositis depends on many factors including the age and diagnosis of the patient, the specific treatment regimen, underlying oral hygiene and genetic factors (2-4). The incidence of oral mucositis in patients receiving chemotherapy ranges from around 40% of patients receiving myelosuppressive chemotherapy for solid tumors to 70-90% of patients receiving myeloablative therapy prior to stem cell transplant (1, 5, 6). A commonly used grading scale for mucositis is the Common Terminology Criteria for Adverse Events (CTCAE version 4.0) grading scale, where grading is based on both subjective and objective assessments on a 5 point scale (Grade 1 to Grade 5).

Adverse Event	1	2	3	4	5
Mucositis Oral Definition: A disorder characterized by inflammation of the oral mucosal.	Asymptomatic or mild symptoms; intervention not indicated	Moderate pain; not interfering with oral intake; modified diet indicated	Severe pain; interfering with oral intake	Life-threatening consequences; urgent intervention indicated	Death

From the Common Terminology Criteria for Adverse Events (CTCAE) Version 4.0 Published: May 28, 2009 (v4.03: June 14, 2010) U.S. DEPARTMENT OF HEALTH AND HUMAN SERVICES National Institutes of Health National Cancer Institute, p. 19

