3.2 Exclusion Criteria

- a. Patients receiving glutamine treatment for oral mucositis.
- b. Patients undergoing autologous or allogeneic hematopoietic cell transplantation are excluded from this study.
- c. Patients receiving concurrent Head & Neck radiation therapy or within 6 weeks of completion of radiation therapy.
- d. Pregnant or lactating patients. The agent used in this study is not known to be teratogenic to a fetus, but has not been studied, and there is no information on the excretion of the agent into breast milk. All females of childbearing potential must have a blood test or urine study within 2 weeks prior to registration to rule out pregnancy.
- e. Known allergy to Caphosol

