4.0 REGISTRATION PROCEDURES

Registration will occur after eligibility is confirmed and the patient/parent has signed the subject consent, but before any treatment has been administered.

The eligibility checklist will be completed at the time of study enrollment.

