5.5 Follow-Up

Study patients will be followed through their first clinic appointment after treatment completion with the appropriate evaluations. Data collection will continue through completion of planned therapy, or until subject meets criteria for removal from protocol therapy or off –study criteria are met as outlined below. Patients who are removed from study per the protocol criteria below, or who withdraw from the study, will not be replaced but will be treated as part of the analysis using either an “intention to treat”, “last observation carried forward” or “by imputation of the missing values”.

Study evaluations will occur each time chemotherapy is received where Caphosol is administered.

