5.6 Criteria for Removal from Protocol Therapy and Off-Study Criteria

5.6.1 Criteria for Removal from Protocol Therapy

- Completion of planned Caphosol therapy (all eligible chemotherapy cycles have been completed)
- Physician determines it is in the patient's best interest
- Adverse Event/Side Effects/Complications which based on the treating physician or patient/family opinion warrant coming off protocol therapy
- Inevaluable
- Patient Intolerance/Refusal

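### Which courses are evaluated, and when data collection ends, is defined by Caphosol use, so the window for detecting Grade ≥2 mucositis can differ between arms in either direction

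*Combined protocol and SAP*

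**What the plan says.** All references are to the combined protocol and SAP.

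- **Entry.** Section 3.2 lists transplant ("Patients undergoing autologous or allogeneic hematopoietic cell transplantation are excluded from this study") and head-and-neck radiation ("Patients receiving concurrent Head & Neck radiation therapy or within 6 weeks of completion of radiation therapy") as exclusions. Section 4.0 places the check at entry: "The eligibility checklist will be completed at the time of study enrollment". Neither event appears among the removal criteria (5.6.1) or off-study criteria (5.6.2).
- **Later courses.** Section 5.4 states: "Caphosol will be continued each time the patient receives chemotherapy where eligibility criteria are met for patients randomized to Caphosol arm". There is no equivalent sentence for controls.
- **Evaluations.** Section 5.5 states: "Study evaluations will occur each time chemotherapy is received where Caphosol is administered".
- **End of data collection.** Section 5.5 also states: "Data collection will continue through completion of planned therapy", or until removal or off-study criteria are met. The first removal item in 5.6.1 is "Completion of planned Caphosol therapy (all eligible chemotherapy cycles have been completed").
- **Arm-neutral text.** The Section 6.0 calendar asks for mucositis grading at each clinic visit and daily during admission, without naming an arm. Section 5.0 gives one treatment period for both arms, and Table 1 repeats it for each arm in nearly the same terms.
- **Analysis.** Sections 10.1 and 10.2 compare incidence on a binary scale. They do not say which courses count, or whether the unit is the patient or the course.

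**The concern.** A fair comparison of ever having Grade ≥2 mucositis needs the same observation window in both arms. Here the window is written in terms of the treatment that only one arm receives.

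This matters most when a patient enrols on a qualifying agent and later goes on to transplant, or has chemotherapy with or soon after head-and-neck radiation. Section 1.0 gives an oral mucositis incidence of about 40% with myelosuppressive chemotherapy for solid tumors, against "70-90% of patients receiving myeloablative therapy prior to stem cell transplant". A few such periods counted in one arm and not in the other could move the primary comparison with no treatment effect behind it. Equally, if controls are evaluated less often than Caphosol patients, control events are missed and a real benefit could be masked.

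**Working it through.** **Step 1. Follow the rules as written in each arm.**

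| Rule | Caphosol arm | Control arm |
|---|---|---|
| Eligibility re-applied to later courses (5.4) | Yes | Not stated |
| Study evaluations (5.5, last sentence) | Courses with Caphosol | Read literally, none |
| Grading calendar (6.0) | Applies | Applies |
| Data collection ends when Caphosol therapy is complete (5.5 with 5.6.1) | Can occur | Cannot occur |
| Data collection ends when planned therapy is complete (5.5) | Applies if reached first | Applies |

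A Caphosol patient whose last eligible cycle is over meets a removal criterion, so data collection can stop before a later transplant. A control in the same position does not meet that criterion, and data collection continues. This is a difference in the stated rules, not only a missing detail.

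**Step 2. Find the direction.** Two readings of the control arm are open.

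- *Reading A:* controls are graded on the Section 6.0 calendar through planned therapy. On a per-patient endpoint, extra observation can only add control events, so the bias favours Caphosol.
- *Reading B:* the last sentence of 5.5 governs. Controls have no course evaluations, control events are under-ascertained, and the bias goes against Caphosol.

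**Step 3. Plan's own figure.** Section 10.3 gives 48 per group for a 30% difference, alpha 0.05 and power 80%. Taking this as 55% v 25%, two-sided:

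n = [1.96·√(2·0.40·0.60) + 0.8416·√(0.2475 + 0.1875)]² / 0.30² = (1.358 + 0.555)² / 0.09 = 40.7, that is 41.

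With the continuity correction this becomes 48, so the figure reproduces on that choice of rates. The point does not depend on it. I use 48 per arm below.

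**Step 4. Illustrate Reading A.**

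- *From Section 1.0:* base rate p = 40% and transplant incidence q = 70–90%. No grade is attached to either figure, so using them for Grade ≥2 is an assumption.
- *Assumed:* a share f of controls graded through a transplant of 5%, 10% or 20% (the documents give none); transplant mucositis independent of earlier mucositis; no true effect; per-patient endpoint; two-sided 0.05 test.

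Control rate = p + f(1 − p)q, and Caphosol rate = p.

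At q = 80%:
- f = 10%: 0.40 + 0.10·0.60·0.80 = 44.8%
- f = 20%: 0.40 + 0.20·0.60·0.80 = 49.6%

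The chance of a significant result favouring Caphosol, by exact binomial enumeration at 48 per arm, is:

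| f | Spurious difference, q = 70–90% | Fisher, q = 70–90% | Fisher, q = 80% | Pooled z, q = 80% |
|---|---|---|---|---|
| 0 | 0 | 1.5% | 1.5% | 2.5% |
| 5% | 2.1–2.7 points | 2.4–2.8% | 2.6% | 4.2% |
| 10% | 4.2–5.4 points | 3.9–5.1% | 4.5% | 6.9% |
| 20% | 8.4–10.8 points | 9.1–13.6% | 11.2% | 15.7% |

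Fisher's exact test is the relevant column, because Section 10.2 names logistic analysis or Fisher's test. The z-test is shown for comparison only.

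**Step 5. Reading B.** The documents give no basis for the number of control events that would be missed, so I put no figure on it.

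**The case against.** The tempting stronger reading is that later high-risk courses count against controls only, so the design makes Caphosol look protective. The documents do not support it, for these reasons:

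- The evaluation sentence in Section 5.5, taken literally, points the other way.
- Section 5.4 concerns duration of therapy. It says when Caphosol is given, not which courses enter the endpoint, and Sections 10.1 and 10.2 do not say either.
- The first item of 5.6.1 needs all eligible cycles to be complete, so an ineligible period between eligible cycles does not remove a Caphosol patient.
- Section 5.5 keeps removed and withdrawn patients in the analysis, by intention to treat, last observation carried forward or imputation.
- Physician discretion and the inevaluable category in 5.6.1 could take a control off protocol therapy before transplant.
- The synopsis gives a study duration of 6–8 months, which may limit how many patients reach such a period.
- Head-and-neck radiation alone is not a chemotherapy course. It matters when chemotherapy is given with it or within 6 weeks after it, and the documents give no mucositis incidence for it.

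All of this stands against a claim of one direction or of a known size. It does not remove the asymmetry. Reading B would leave the control arm without endpoint evaluations and conflicts with the arm-neutral calendar in Section 6.0, so Reading A is the more workable one; but the text does not choose. Discretionary removal is not a common rule for both arms, and no placebo or blinding is described, so such decisions may be made with the arm known. Keeping removed patients in the analysis does not supply gradings that were never collected.

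**Conclusion.** The point holds in this form: course eligibility, evaluations and the end of data collection are written around Caphosol use, so ascertainment of Grade ≥2 mucositis can be unequal between arms. The direction is undetermined. A reader might infer that the bias necessarily favours Caphosol, but that follows only under Reading A.

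The size is unknown. The rise in false-benefit probability from 1.5% to about 4.5% or 11.2% is an illustration. It rests on an assumed 10% or 20% share of controls graded through transplant, 40% and 80% incidences applied to Grade ≥2, and independence from earlier mucositis. Nor would these periods redefine the trial's population: only the unknown share of patients who reach them is affected.

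The plan should be corrected, because the rules as stated cannot be applied equally to both arms and the correction is cheap.

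**What to change.** Define the study course and the grading window identically for both arms in Sections 5.4, 5.5 and 5.6.1. Possible wording:

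*In either arm, a study course is any chemotherapy course containing an agent listed in 3.1a that is not given as part of hematopoietic cell transplantation and is not concurrent with, or within 6 weeks after, head-and-neck radiation. Study evaluations follow the Section 6.0 calendar in every study course in both arms. Endpoint data collection ends in both arms when all study courses are completed.*

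Then:

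- In 5.5, replace the clause that ties study evaluations to Caphosol administration.
- In 5.6.1, reword the first item so that a patient in either arm can meet it.
- Do not re-apply the whole of 3.1 and 3.2 to later courses. The 3.1 requirement that patients be starting their oncology therapy would disqualify every later course. The glutamine exclusion would drop courses because of earlier mucositis, which is selection on the outcome. Record glutamine started after entry as a co-treatment.

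This governs which data count, not how patients are treated. The cost is wording in three sections, a short check at each course in both arms, and slightly shorter follow-up in a few patients.
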